6 CONSENT

Potential participants will be approached via telephone during their planned preoperative andrology telephone appointment prior to their surgery date. They will receive an electronic PIS sent via NHS email or post. They will have at least 24 hours to read the study, reflect on the information provided and have the opportunity to ask questions. During their hospital hospitalisation, a selected member of the clinical team will approach them again and provide them with the opportunity to ask any questions and sign the consent form for those agreeing to enrol in the study.

Patients may express interest by phone, but formal consent will only be obtained in writing after discussion with the research team.. The electronic consent platform will be developed within the RedCAP service hosted behind the UCL Data Safe Haven, which conforms to NHS Data Security & Protection Toolkit, General Data Protection Regulation, and ISO 27001 Information Security. Patients cannot sign consent until a face-to-face (or secure e-consent) discussion with the research team.

A copy of the consent form will be given to the patient, a copy uploaded to the electronic health records of the patient and the original will be stored in the ISF. All members of the team consenting patients will be suitably qualified, experienced, and will have been delegated this duty by the CI/ PI on the Staff Signature and Delegation of Tasks.

When the participant receives the participant information sheet (PIS), it will be recorded in the patient's medical notes (or electronic health record). The PIS and consent form will be reviewed and updated, if necessary, throughout the study (e.g. where new safety information becomes available) and participants will be re-consented as appropriate.

At every review at regular intervals, patients will be given the opportunity to withdraw from the research study.

Electronic Consenting

The electronic consent platform will be developed within the RedCAP service hosted behind the UCL Data Safe Haven, which conforms to NHS Data Security & Protection Toolkit, General Data Protection Regulation, and ISO 27001 Information Security.

7 DATA ANALYSIS

Univariate and multivariate regression models looking at the imaging parameters values, video quality ratings, baseline EF scores to predict EF scores at 12 months. Correlation coefficients between the imaging parameters values, video quality ratings, baseline EF scores to predict EF scores at 12 months intervals. Interobserver discordance will be arbitrated by a third independent reviewer. We will utilise the data management software R to carry out the statistical analysis.

To address missing data in validated erection function questionnaires, we will use Multiple Imputation (MI), a widely accepted method that handles missing data under the Missing at Random (MAR) assumption. MI imputes missing values multiple times to create several complete datasets, which are analysed separately, and results are pooled using Rubin's rules to incorporate imputation uncertainty. This approach retains all participants, preserving statistical power and minimizing bias. We will use the mice package in R to perform MI, incorporating clinically relevant variables such as baseline characteristics and prior questionnaire responses, with diagnostic checks ensuring plausible imputations. This method is robust, scientifically sound, and commonly used in observational studies.

8 PATIENT AND PUBLIC INVOLVEMENT (PPI)

We have identified three patients who have had NVB sparing surgery at UCLH and discussed the study with them sharing the lay summary of the research, study design and PIS and consent forms. We also discussed with them their perception of the electronic consenting as well as electronic data collection. They confirmed the suitability and feasibility of the study from a patient perspective.

9 FUNDING AND SUPPLY OF EQUIPMENT

The study funding has been reviewed by the UCLH/UCL Joint Research Office and deemed sufficient to cover the requirements of the study. NHS costs will be supported via UCLH and/or the Local Clinical Research Network.

[name] research fellow- his time has been fully funded and costed. The penile doppler US will be carried out by [name] who is trained to carry out penile doppler US.

Funding has been acquired for the postoperative MRI. The costs will only be required for carrying out the MRI as the reporting will be done free of charge by the uro-radiologist which are part of the research team.

10 DATA HANDLING AND MANAGEMENT

The study is compliant with the requirements of General Data Protection Regulation (2016/679) and the UK Data Protection Act (2018). All investigators and study site staff will comply with the requirements of the General Data Protection Regulation (2016/679) with regards to the collection, storage, processing and disclosure of personal information, and will uphold the Act's core principles. UCL is the data controller; the UCL Data Protection Officer is [contact]. The data processors are [[name], [name]]. The study will be collecting the following personal data:

-Patient data: Basic patient information will be kept including hospital numbers, names and date of births. This will be the key and will be kept in a separate file. All other data collected will (non-identifiable information) will be in pseudonymised fashion in a separate sheet. All files will be password protected. MRI markers will be kept as part of the pseudonymised data sheet. The questionnaires will be scanned and uploaded onto the individual patient electronic records. Consent forms are discussed in section 6.

A study key including a list of participants (identified by their hospital number) along with the corresponding trial personalised identification number will be stored in a file on a secure computer in Westmoreland Street Hospital, UCLH NHS Trust, under one login. This is in a locked office. This file will be password protected. Any paper questionnaires and consent forms will be stored in the locked office at UCLH. The EF questionnaires will be scanned and uploaded onto the individual patient electronic records. When the consent form is complete, 1 will stay with the participant; 1 for researcher site file; 1 to be kept in medical notes electronically.

-The video recordings: This will be done through the standard operating stack and require no additional steps to changes to standard care. Currently, the procedures are routinely recorded in the operating room for training purposes and to evaluate where improvements could be made. We do not anticipate that there will be any new material ethical issues associated with the recording

EVERiST, EDGE (Sponsor) number 177704, IRAS number 335003, Protocol version 1.0, 07/10/2025

system. The videos will be entirely anonymised so no patient identifiable information will be available on the actual video. In the file name, it will have a study number. The study number will be the pseudonymised. The key will only be kept at a UCLH NHS computer. All files will be password protected. The videos will be uploaded to the password protected file on NHS one drive. They will have no identifiable information. When they are edited, they will be presented to other NHS surgeons who perform RARP through the NHS drive. The surgeons will rate the quality of the videos but will view no identifiable information and will not be able to download the videos.

-The postoperative MRI will be stored on university drive and may be used in other studies.

PEER AND REGULATORY REVIEW

The study has been peer reviewed in accordance with the requirements outlined by UCL.

The study was deemed to require regulatory approval from the following bodies (NHS REC Favourable Opinion and HRA Approval). **Before any site can enrol patients into the study**, the Chief Investigator/Principal Investigator or designee will ensure that the appropriate regulatory approvals have been issued, and NHS Confirmations of Capacity and Capability and Sponsor green lights are in place.

For any amendments to the study, the Chief Investigator or designee, in agreement with the Sponsor, will submit information to the appropriate body in order for them to issue approval for the amendment. The Chief Investigator or designee will work with sites (R&D departments as well as the study delivery team) to confirm ongoing Capacity and Capability for the study.

All correspondence with the Sponsor, REC and HRA will be retained. The Chief Investigator will notify the Sponsor and REC of the end of the study.

It is the Chief Investigator's responsibility to produce the annual progress reports when required; an annual progress report (APR) will be submitted to the Sponsor and REC within 30 days of the anniversary date on which the favourable opinion was issued, and annually until the study is declared ended.

If the study is ended prematurely, the Chief Investigator will notify the Sponsor and REC, including the reasons for the premature termination.

Within one year after the end of the study, the Chief Investigator will submit a final report with the results, including any publications/abstracts, to the Sponsor and to the REC and HRA.

11 ASSESSMENT AND MANAGEMENT OF RISK

-Data management risks are discussed in section 10.

-Video recordings: This will be done through the standard operating stack and require no additional steps to changes to standard care. Currently, the procedures are routinely recorded in the operating room for training purposes and to evaluate where improvements could be made. The management of the video data file is discussed in section 10.

-Hospital visits: for participating patients, an additional MR angiogram will be obtained postoperatively for study participants which will require an additional visit to the hospital. The remaining appointments will align with the standard andrology follow-up after radical prostatectomy.

-Penile dopplers (OPTIONAL) A penile doppler US will be offered to patients before and after surgery to assess the erectile machinery for study participants. This will be particularly useful for patients that fail to achieve satisfactory erections with medical treatment after surgery. A large proportion of patients that fail medical treatment and wish to escalate their erectogenic treatment will require injection treatment to the side of the penis. During the tutorial for this therapy, we will carry out a penile doppler ultrasound to assess their EF objectively and assess the blood flow to the penis.

The use of penile dopplers will require injection into the penis with Alprostadil or Invicorp (phenotmaline and aviptadil) which are an erection inducing medication. Both of these injections are commonly used to treat ED especially in men with radical prostatectomy so a significant proportion of men will have an injection after surgery in non-research setting. The commonly used trade name for alprostadil is VIRIDAL DUO or CAVERJECT. This carries a small risk of a prolonged painful erection which is a urological emergency if lasts more than 4 hours (risk of 1% with alprostadil or 0.3% with invicorp). Patients will be consented again and will have the right to withdraw their consent to have this investigation. Patients will be monitored for at least 2 hour after their ultrasound to ensure their erection is reducing before they go home. If they do develop a prolonged erection, they will be offered treatment by the research andrology team promptly prior to developing a priapism. This will ensure that no patient will develop priapism after these penile doppler US. Careful safety netting will be provided for patients and advice to seek urgent urological care if they develop a prolonged painful erection.

11.1 RECORDING AND REPORTING OF EVENTS AND INCIDENTS

All events and incidents (and near misses) that occur to participants and/ or staff that are **unexpected** and directly **related** to the research study will be reported to the Sponsor via UCL: [contact] or [UCL REDCAP incident reporting form](#)) and host sites via their Trust reporting systems, and documented in the Trial Master File/Investigator Site File via study-specific incident logs (and related correspondence). This will be completed by the CI or PI. The Sponsor will be responsible for investigating, reviewing, or escalating to a serious breach if required.

Definitions

Term	Definition
Adverse Event (AE)	Any untoward medical occurrence in a patient or trial participant, which does not necessarily have a causal relationship with the intervention involved.
Serious Adverse Event (SAE).	Any adverse event that: 
• results in death,• is life-threatening*,• requires hospitalisation or prolongation of existing hospitalisation**,

	
 • results in persistent or significant disability or incapacity, or • consists of a congenital anomaly or birth defect. • Other 'important medical events' may also be considered serious if they jeopardise the participant or require an intervention to prevent one of the above consequences

* A life- threatening event, this refers to an event in which the participant was at risk of death at the time of the event; it does not refer to an event which hypothetically might have caused death if it were more severe.
 
** Hospitalisation is defined as an in-patient admission, regardless of length of stay. Hospitalisation for pre-existing conditions, including elective procedures do not constitute an SAE.
	

3.1. Assessments of Adverse Events

Each adverse event (AEs) will be assessed for severity, causality, seriousness and expectedness from consent to 90 days post op as it unlikely any SAEs past this point will be related to surgery. Adverse event assessment will be carried out using the patient electronic clinical records. This will reduce site reporting workload. Trial follow up should continue according to schedule once the SAE is resolved, if applicable.

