3.7 Assessment of the pelvic vasculature with a postoperative an MR angiogram

By obtaining an MR angiogram with an arterial phase after the surgery, we will be able to confirm whether there is blood flow in the accessory pudendal arteries after surgery. This additional MRI at least 3 months after surgery will be only offered to patients who have an accessory pudendal artery on their preoperative mpMRI. This will be useful to assess whether the APA patency after surgery has an effect on EF outcomes. If there is an incidental finding on this MRI relating recurrence, then the parent team and the CI will be notified promptly. This will lead to further appropriate action.

We will follow an established and validated protocol for MRI angiography on month 3 (described in Appendix)

3.8 Penile doppler US (optional): Objective assessment of EF using erectile haemodynamics.

Penile Doppler ultrasound (PDUS) is a well-established diagnostic tool for ED in specialist clinical practice. As an optional part to the study, we will offer patients an opportunity to assess their erectile haemodynamics prior to surgery through a PDUS. The APA presence, features or absence will be known through review of their preoperative mpMRI. With that knowledge, the optional PDUS before surgery will outline the effect of APA on the haemodynamics in healthy men with prostate cancer.

Patients who will not respond to PDE5i after surgery will be offered with a PDUS to evaluate the flow of penile arterial blood and to provide objective evidence that the underlying cause of ED is arterial.

This will be an optional part to the study and will be offered at 6 months or earlier if patients wish to have ICI to treat their ED. This is the accepted standard of care for the evaluation of post-RARP ED that is not responding to medical treatment.

The standard penile doppler US protocol will be followed for patients who opt for this assessment. Details of the protocol are provided in appendix.

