Blood tests: The metabolic assessment of ED includes testosterone, HbA1c and lipid profile biochemical profile. As part of routine post-surgical PCa follow-up all patients have a PSA tests done
EVERiST, EDGE (Sponsor) number 177704, IRAS number 335003, Protocol version 1.0, 07/10/2025

at 2 to 3 months and either 1 or 3 more until month 12 depending on cancer features. We will use these time points to obtain the blood samples required for assessment of ED. Hence, additional hospital visits will be avoided. These blood samples that will be requested are standard part of assessment of ED therefore not leading to additional NHS costs. If the metabolic ED blood panel is normal, this will not be repeated again. Any abnormalities in these will be communicated to the patient and their general practitioner and where necessary, treatment will be recommended i.e. if patients have a new diagnosis of diabetes, the patient and their general practitioner will be informed to repeat the test and start treatment if necessary. These will then be retrospectively recorded by the research team. No samples will be obtained or stored as part of this research.

Postoperative MRI: For patients that undergoing bilateral NVB sparing RARP, with an APA identified on their preoperative mpMRI, an additional MRI will be offered at least 3 months after surgery to assess whether the accessory artery was preserved or sacrificed.

Penile doppler US: For patients opting to undergo a PDUS before and after surgery, an additional hospital visit may be required prior to surgery to perform the preoperative PDUS. Postoperatively, if patients do not respond to oral medication treatment for ED, they will be offered a PDUS during the same visit as their tutorial for intracavernosal injection (ICI) therapy, minimizing the need for additional hospital visits.

This tutorial, conducted in the clinic, ensures patients are proficient in self-administering alprostadil or Invicorp to achieve an erection. This approach aligns with the current standard of care for patients unresponsive to oral medications. During the clinic session, a penile Doppler US will be performed in conjunction with ICI self-administration to assess erectile haemodynamics comprehensively.

Additional visits:

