11.3 Adverse Events and Serious Adverse Events Sponsor Reporting Requirements (if applicable)

Adverse events are any untoward medical occurrence in a patient or study participant, which does not necessarily have a causal relationship with the procedure involved. These do not require reporting to the Sponsor, but the severity, causality and expectedness will be recorded in the participant's medical records, CRF and AE log, with a description of clinical symptoms and the event, including dates as appropriate.

SAEs (any event that results in death, is life-threatening, requires hospitalisation or prolongation of existing inpatient hospitalisation, results in persistent or significant disability or incapacity, or consists of a congenital anomaly or birth defect) that have been determined to be **unrelated** to the research intervention by the CI/PI do not require reporting to the Sponsor, but will be recorded in the participant's medical records, CRF and site file. Additionally, **expected** SAEs that are likely to occur on a regular basis and offer no further new information to the safety profile, or are related to the disease area of the participants, do not require reporting to the Sponsor, but must be recorded as previously stipulated. Sponsors will however be notified where the frequency and severity of unrelated SAEs are unusual; research sites will report as per Sponsor reporting requirements.

In some instances, **unexpected and related SAEs** may occur in observational research [for example, Claustrophobia during MRI scans, allergic reaction with contrast agent during MRI or towards medications during scans]. All reportable SAEs will be recorded in the medical records and CRF, and reported to the Sponsor via the [JRO REDCAP research incident reporting form](#) or [contact], within 5 working days of becoming aware of the event. The Chief or Principal Investigator will respond to any SAE queries raised by the Sponsor as soon as possible.

All adverse events will be recorded in the medical records in the first instance. All related adverse events will be recorded in the CRF until 90 days after surgery.

All related adverse events will also be recorded on the non-CTIMP Adverse Event (AE) log, and stored in the site files.

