All serious adverse events related to the intervention will be recorded in the medical records and the CRF, and the sponsor's SAE log. The AE and SAE logs will be stored in the TMF Investigator Site File and may be subject to Sponsor monitoring and auditing.

All SAEs (except those specified in the protocol as not requiring reporting to the Sponsor) will be reported to the Sponsor within 24 hours of becoming aware. The CI/PI or designated individual will complete the Sponsor's online Research Incident Reporting Form (<https://redcap.slms.ucl.ac.uk/surveys/?s=NE5dypTdFo>) within 24 hours of becoming aware of the event. The Chief or Principal Investigator will respond to any SAE queries raised by the Sponsor as soon as possible.

In the first instance, research participant complaints (patients or health volunteers) will be reported to the CI/PI to investigate, as documented in the patient information sheet(s), and to the Sponsor via [contact], following the *UCL Complaints from Research Subjects about UCL Sponsored Studies and Trials* policy. For participants who are NHS patients, complaints will be reported to the NHS Complaints Manager at the Trust where the recruitment and study procedures were undertaken. Complaints from NHS patients are handled under NHS complaints policies and procedures, with involvement from PALS and the Sponsor where necessary.

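### Adverse-event assessment and CRF recording are dated to stop 90 days after surgery, before most study-added post-operative procedures; undated rules conflict with this, and SAE reporting has two deadlines

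*Protocol*

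**What the plan says.** **The dated rules.** Assessments of Adverse Events (numbered 3.1, within section 11.1) limits the assessment of each event's severity, causality, seriousness and expectedness to the period "from consent to 90 days post op as it unlikely any SAEs past this point will be related to surgery". Section 11.3 adds: "All related adverse events will be recorded in the CRF until 90 days after surgery".

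**The timing of the procedures.** Section 4 says that, for men with an accessory pudendal artery (APA) on the pre-operative scan, "an additional MRI will be offered at least 3 months after surgery to assess whether the accessory artery was preserved or sacrificed". Section 3.7 uses the same lower limit. Elsewhere in sections 3.7 and 4 the angiogram is placed simply at month 3. Section 3.8 says the post-operative penile Doppler ultrasound (PDUS), which involves an intracavernosal injection, "will be offered at 6 months or earlier if patients wish to have ICI to treat their ED".

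**The undated rules.**
- Section 11.1 sends unexpected, related events and incidents to the sponsor and to incident logs.
- Section 11.3 opens by placing the severity, causality and expectedness of adverse events in the medical records, CRF and AE log.
- Section 11.3 later sends all related events to the non-CTIMP AE log, and related SAEs to the medical records, CRF and SAE log.

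**The SAE deadlines.** Section 11.3 first asks for reportable SAEs "within 5 working days of becoming aware of the event". It later says that all SAEs not exempted by the protocol "will be reported to the Sponsor within 24 hours of becoming aware".

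**The concern.** The window is justified by the operation, but the operation is not what the study adds. Table 1 lists prostatectomy under the standard clinical schedule, and section 3 calls the study non-interventional. After surgery, the study's own exposures are the gadolinium angiogram and, in part, the PDUS. The protocol foresees harms from both: section 11.3 mentions claustrophobia, contrast allergy and drug reactions during scans, and section 11 describes prolonged painful erection after the injection.

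The angiogram and the post-operative PDUS are the subject of primary end-points 5 and 7, and section 1.2.7 says their practicality will inform a larger study. If staff follow the dated rules, structured safety data would stop just before most of this exposure begins. The tolerability record passed to the future study would then be incomplete in a favourable direction.

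The SAE deadlines raise a second, separate question: which limit makes a report late?

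**Working it through.** The plan gives no figure to reproduce. The check compares dates and then sets the rules side by side.

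**1. Angiogram against day 90.** Inputs: a lower limit of 3 months (sections 3.7 and 4) and a cut-off at day 90. Assumption: surgery on any date from 1 December 2025 to 30 November 2026, that is, the expected start plus the 12 months of recruitment in section 3. Adding three calendar months to each of the 365 dates gives:

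| Days to 3 months | Surgery dates |
|---|---|
| 89 | 29 |
| 90 | 62 |
| 91 | 63 |
| 92 | 211 |

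The earliest permitted scan is after day 90 for 63 + 211 = 274 of 365 dates (75%). It is on or after day 90 for 274 + 62 = 336 of 365 (92%). These are earliest dates; under the lower-limit wording, scans can only be later.

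**2. PDUS against day 90.** Six calendar months is 181 to 184 days over the same dates, so a 6-month PDUS takes place 181 − 90 = 91 to 184 − 90 = 94 days after the window closes. An earlier post-operative PDUS may fall inside it. A pre-operative PDUS after consent is covered.

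**3. Follow-up outside the window.** Twelve months is 365 days, so 365 − 90 = 275 days of follow-up lie beyond the cut-off.

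**4. Number of angiograms.** Section 1.2.4 gives an APA prevalence of 38.2%, and the target is 20 to 40 men. If mpMRI detects APAs at that rate and every man accepts: 0.382 × 20 = 7.6 and 0.382 × 40 = 15.3, or about 8 to 15 angiograms.

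**5. Prolonged erection, as an upper illustration.** Section 11 gives a risk of 1% with alprostadil or 0.3% with Invicorp. If every man had one post-operative PDUS, the chance of at least one event is 1 − (1 − p)^n:

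| n | p = 0.01 | p = 0.003 |
|---|---|---|
| 20 | 18% | 6% |
| 40 | 33% | 11% |

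PDUS is optional, and after surgery section 3.8 directs it to men who do not respond to oral treatment, so the true chances are lower.

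**6. What happens to an event after day 90.**

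| Event | Dated rules | Undated rules |
|---|---|---|
| Related, non-serious | no assessment, no CRF entry | medical records, AE log; CRF under the opening of 11.3 |
| Related SAE | no assessment | medical records, CRF, SAE log; sponsor if reportable |

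The two columns disagree. The undated routes also depend on someone having judged the event to be related, serious or unexpected, and that judgement is what the dated assessment rule ends at day 90.

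**7. SAE deadlines.** Ignoring public holidays, 5 working days is 120 to 168 elapsed hours depending on the weekday, which is 5 to 7 times 24 hours. Both limits run from awareness, both use the sponsor's incident form, and they cover in substance the same SAEs. A report made on the third day meets one sentence and breaches the other.

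**The case against.** A reader might infer that harms from the angiogram and PDUS are simply lost after day 90. The protocol does not support that. The undated sentences still place related events in the medical records and AE log, and unexpected related ones in incident logs. Contrast allergy and reactions during scans are named as examples of SAEs, and the sentence that follows sends reportable SAEs to the CRF and sponsor with no 90-day limit. A prolonged erection that needed intervention might also qualify as an SAE. This stands, and it reduces the point to a conflict between rules, with non-serious events most exposed.

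The post-operative PDUS is only partly a study procedure. Sections 3.8 and 4 call it standard of care for men who do not respond to oral medication and attach it to the injection tutorial. It may also take place before day 90. This stands too, so the angiogram is the stronger example.

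Safety is not an end-point. End-points 5 to 7 count acceptance, receipt and APA patency, none of which uses adverse-event counts. That is correct: no primary estimate changes. What suffers is the safety record that accompanies those estimates.

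Finally, a reader might infer that staff cannot comply with both SAE deadlines. They can, because a report within 24 hours also falls within 5 working days. The fault is a contradictory standard.

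**Conclusion.** The point holds as a conflict within the protocol. As written, the dated rules end structured assessment and CRF recording of related events at day 90, on reasoning that considers only surgery. Nearly all study-added angiograms, and any PDUS done at 6 months, fall at or after that day. Undated sentences say otherwise for some or all of these events, so the outcome depends on which sentence staff follow. Non-serious procedure-related events are the ones most likely to be left out.

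The size is about 8 to 15 angiograms, assuming 38.2% prevalence, detection by mpMRI at that rate and full acceptance. The prolonged-erection figures (6 to 18% for 20 men, 11 to 33% for 40) are ceilings that assume one post-operative PDUS per man; they do not forecast missed events. Nor can it be said that every angiogram falls outside the window: three calendar months can be day 89 or 90.

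The two SAE deadlines are a separate contradiction. The protocol does not show which one is intended.

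**What to change.** - Amend Assessments of Adverse Events and the dated CRF sentence in section 11.3 so that events related to the angiogram or PDUS are assessed and entered in the CRF whenever the procedure takes place, up to the last study visit. Name that visit: the end-of-study definition uses 12 months, while sections 3 and 3.5 also mention 24.
- Keep the 90-day limit for surgery-related events, for which its reason was written.
- Align the undated sentences in sections 11.1 and 11.3 with the amended window, so that one rule governs each class of event.
- Have the sponsor reconcile the two SAE reporting deadlines in section 11.3 into one.

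The cost is protocol wording and a few extra CRF entries. No procedure, visit or end-point changes.
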